3. STUDY DESIGN

Prospective Observational, Non-interventional, Study: Analysis of the recordings of Somatosensory Evoked Potentials test which is performed for prognostication in Derriford intensive Care Unit, in comatose survivors after Out of Hospital Cardiac Arrest. The interpretation of the recordings will include the presence or absence of P25/30 SSEPs, of N20 SSEP and possible other short or long latency evoked potentials on these recordings. After the interpretation of the recordings then a test for possible correlations of the recorded P25/30 SSEPs with the neurologic prognosis of the survivors will be performed.

Estimated Study Duration: 24-36 months

Estimated Number of patients: One hundred and twenty adult Intensive Care Unit patients. In order to be included in the study, all patients must be adults, comatose survivors after out of hospital cardiac arrest who are admitted to Derriford Intensive Care Unit.

3.1 STUDY OUTCOME MEASURES

Primary Endpoint: Neurologic outcome assessed by Cerebral Performance Category [CPC] score at hospital discharge.

Secondary endpoints: Mortality at hospital discharge and at 28 days [which occurs first], comparison of prognostic benefit of N20 and P25/30 SSEPs-based multimodal prognostic models.

4. PARTICIPANT ENTRY

4.1 RECRUITMENT AND CONDUCTION OF THE STUDY

The general management of adult comatose survivors after OHCA, who are admitted to the Derriford ICU, consists of provision of organ support as required [mechanical ventilation, cardiovascular support, renal replacement therapy], targeted temperature management aiming to maintain patients in normothermic condition for the first 72 hours, continuous invasive and non-invasive multimodal monitoring [vital signs, respiratory and haemodynamic monitoring, neurologic monitoring] and treatment of the underlying cause of cardiac arrest [if known-diagnosed]. The patients remain sedated for the first 36 hours to facilitate brain protection, optimisation of patient's organ function parameters and achievement of targeted temperature within very strict temperature limits [For the first 24 hours temperature target is 36°C and for the next 48 hours the temperature target is 36-37°C]. The targeted temperature management is achieved with the use of external cooling devices. The neurologic prognostication of the post cardiac arrest patients is mainly based on a multimodal approach guided by the clinical picture of the patient [Level of consciousness, Glasgow Coma Scale, presence or absence of reflexes and focal neurologic signs], the results of the CT imaging studies [CT or MRI of the Head], the results of the Electroencephalogram and SomatoSensory Evoked Potentials [SSEPs] recording which usually are performed after the first 24 hours post ROSC. The SSEPs recording are performed in all comatose survivors after OHCA who are admitted to Derriford ICU as an integral part of their normal care. The recording and the analysis of the recording are conducted by the members of the neurophysiology team in Derriford Hospital. The main aim of that routine, established and used for the last 3 years, prognostication test is to assess the presence or absence of the N20 SSEP in comatose survivors after out of hospital cardiac arrest. According to the international medical literature and the national guidelines, N20 presence is associated with unknown [ranging from full neurological recovery to severely disabled status] neurological prognosis, whereas N20 absence is always reliably associated with poor neurologic prognosis.

During our study, we will interpret further the results of the SSEP recordings not only for N20 but also for the presence or absence of the P25/30 SSEPs and we will test if they are related with patients' neurological prognosis. No consent is required for the SSEP recording as this is a part of the normal clinical care of the patients in Derriford ICU and has been already used for years in daily clinical practice of our unit, as a useful tool for the neurologic prognostication of post cardiac arrest patients.

During the study, consent will be required only for the additional interpretation of the SSEP recording sheet, regarding the presence or absence of P25/30 SSEPs and their potential prognostic significance. Nothing in the post cardiac arrest ICU management changes because of the study as no additional intervention and no additional tests will be introduced further to the normal care of the ICU patients that is established currently [figure 3].

Explaining that in further details: On the admission to Derriford ICU [Penrose and Pencarrow wards], all adult comatose survivors after OHCA will be managed according to the already established routine Derriford ICU protocol for the management of all patients after out of hospital cardiac arrest.

According to the current ICU routine care protocol: the patients will remain sedated for the first 36 hours as per ICU policy. As per normal ICU care, the sedatives that will be administered as a continuous infusion will be propofol [at a rate of 1-4mg/kg/h] and fentanyl [at a rate of 50-200mcg/h]. Midazolam infusion would be used only if the use of propofol is could not be tolerated due to severe haemodynamic instability or adverse effects to propofol developed. Neuromuscular Blocking agents [Atracurium or Rocuronium] may intermittently or continuously be administered to the patients, if required, for the management of their ventilation and / or for the control of severe rigor during the targeted temperature management and / or for the control of myoclonus or convulsions.

The reasons that the patients remain sedated for the first 36 hours are to facilitate brain protection, to optimise patient's organ function parameters and to achieve targeted temperature management within very strict temperature limits.

According to the Targeted Temperature Management protocol of the Derriford ICU, the body temperature will be maintained at 36°C for the first 24 hours and between 36-37°C for the next 48 hours up to a total of 72 hours. As per ICU management practice, organ support as required [mechanical ventilation, cardiovascular support, renal replacement therapy], continuous invasive and non-invasive multimodal monitoring [vital signs, respiratory and haemodynamic monitoring, neurologic monitoring] and treatment of the underlying cause of cardiac arrest [if known-diagnosed] will be provided. The targeted temperature management is achieved with the use of external cooling devices.

Between the 24 hours and the 36 hours after ROSC, the usual SSEP recording will take place in ICU by members of the neurophysiology team. The recording will be performed, as usual and normal ICU care without any modification for the study, while patients are on sedation [as described above]. The use of neuromuscular blocking agents will be applicable if indicated for any of the aforementioned clinical reasons or in order to achieve the best recording quality [clear recording of SSEP baseline in patients to facilitate the optimal interpretation of the recording mainly in patients with tremor or myoclonus] if that is not possible to be achieved while patients are on sedation. A single dose of Atracurium or Rocuronium will be administered for this purpose only if this is absolutely necessary. The Neurophysiology team members may request the use of neuromuscular blocking agent if they

think that the quality of their recording is poor. It will be the decision of the ICU consultant in charge if the neuromuscular blocking agent could be administered.

Within the first 24 hours in the ICU the patients will be assessed by the members of the research study team regarding their eligibility to be enrolled in the study. If the patients meet the specific inclusion and exclusion criteria for the study, their next of kin [NOK] will be approached by a member of the research team [who is also a member of the ICU clinical team] at ICU. All NOK will be spoken to in person. A full explanation of the study design, of the study protocol and of the study objectives, as well as a specific relative information leaflet containing all the information for the study, will be provided. The provision of informed consent by the NOK will be requested if patients meet the eligibility criteria for study enrolment. The meeting with the NOK may be done ideally before the SSEP recording or, in case of non-availability of the NOK, after the SSEP recording.

During the informed consent process, the members of the study group will actively listen to the thoughts of the next of kin, and they will try to provide the maximum information to them not only about the study but also about the general potential benefit for the patients by research, the importance of the research in modern medicine and specifically in the specialty of Intensive Care Medicine where many clinical and prognostic uncertainties still exist.

The next of kin for each potential participant will be asked to consent for the participation of the patients in the study, after being fully informed both verbally and by the provision of the relevant Trial Participant Information Sheet and a copy of the Trial Informed consent form that can be found in the appendix of this document. The patient will also be given the contact details of the ICU Research Nurse, should they wish to seek further information about the study. In most cases, the next of kin of potential participants will have at least 24 hours to decide whether or not to participate in the study.

Method of SSEP recording – Neurophysiology Data Acquisition and Interpretation

The following protocol of N20 SSEP recordings, currently used in Derriford ICU, will be applied for the purpose of the study. N20 and P25/30 SSEPs are expected to be recorded and then during the study interpretation of the results the presence or absence of either or both and the correlation between them will be assessed

Neurophysiology protocol of Somatosensory Evoked Potentials [upper limb Median/ Ulnar] in Derriford ICU following Out Of Hospital Cardiac Arrest.

This protocol has been used successfully for SSEP recording in Derriford ICU since 2015. This is part of the usual, established Derriford ICU policy for the management of the comatose survivors after out of hospital cardiac arrest and is not added or at any way modified, because of the study. The study purpose is the interpretation of the recording sheet of the SSEP test in order to answer the question whether the P25/30 potential that is recorded along with the N20 may have prognostic significance for the patients' neurological outcome.

The protocol of the SSEP recording is described below in details:

Deymed evoked potential system is used

Open Acquisition

Open EP protocol and select SEP from list

Select Median 4 Channel Right or Left depending on side being tested

Press On which brings up live trace to monitor

Turn up stimulation until a visible thumb twitch is seen, then select average; wait until at least 500 samples has been performed on each channel.

Measure wave forms accordingly using the measuring tool, - to print the waveforms press Quick report this will bring up document to print and then press the print icon.

A note of the patient's height if known should be made in cm.

Any sedative medication being used must be recorded on the request form. Patient should be paralysed with muscle relaxant agent to minimise EMG/movement artefact

Stimulation is routinely performed of the median or ulnar nerve in the hand; however this can be modified where necessary.

Machine Settings:	Stimulus Settings	Amplifiers (Default)
	Duration 0.1ms	Sensitivity 20-50uV/division
	Rate 2.9Hz	Low frequency Filter 20Hz
		High Frequency Filter 2KHz
		Notch Off
		Artefact rejection On 20uV Divisions (Channel must be selected individually)
		Impedance Value must be below 5Kohm.

The machine settings may be altered as the physiologist doing the test sees fit

Electrode Placement	Position	Label (headbox)
Mid clavicle	Erb's point	Channel 4 Ipsilateral/contralateral Erbs
Nape of neck	CV2	Channel 2
Over prominent spinous process	CV7	Channel 3
	Cortex (2cm posterior to Cz and 6cm lateral on contralateral hemisphere)	Channel 1 C3/ C4
	Fz reference	Fz + input
	Ground strap on limb tested	Ground (linked)

Montage	Channel 1	Fz – C3/C4
	Channel 2	Fz/Front neck ref – Cervical C2
	Channel 3	Fz/Front of neck – Cervical C7
	Channel 4	Fz/lps/ContErb – Erbs Ips/Cont

Sweep time: 100ms

Recording procedure

SSEPs must be recorded after at least 24hours following ROSC. Usually to be performed between 24-36 hours after ROSC.

Temperature must be recorded; mild to moderate hypothermia $\geq 36^{\circ}\text{C}$ does not abolish the cortical N20 responses. Cortical responses have been proven to remain until a nasopharyngeal temp of 20°C is reached.

The N20 remains present even at a sedation level sufficient to induce an iso-electric EEG.

Running the test

The established, used for many years in Derriford ICU, SSEP recording protocol is used. No changes in terms of either the method of recording or the length of the test would be done as a result of the study. Besides, the study does not have to do anything with the SSEP recording but with the further interpretation only of the recording paper for evidence of other potentials that could be used for prognosis.

The patient is positioned to reduce muscle artefact. If this is not possible and muscle artefact is high muscle relaxants may need to be prescribed to improve quality of recording and quality of SEP, especially in cases where it is thought to be absent.

The level of stimulation is subjective and needs to elicit a visible twitch of the appropriate muscle. Therefore this should be achieved prior to administration of muscle relaxant

Averaging begins once adequate stimulation is achieved, a minimum of 500 trials is required, and this must be increased where necessary. A minimum of two trials must be recorded to check for reproducibility.

Interpretation of the recording regarding N20s at the bedside for clinical purposes. This is part of the current established normal ICU care and is not part of the study.

Cortical N20 response is to be described as bilaterally absent (which is a good predictor of poor neurological outcome), or in other cases in may be present on one or both sides.

If the cortical N20 response is absent, the presence of the peripheral N9 and N13 response must be present to ensure that the response has arrived at the cortex. Cervical lesions need to be excluded if Cortical N20 response is absent. Immediately after SSEP recording, each recording will be interpreted for N20 and the result will be disclosed to the ICU clinicians as currently happens in the context of the ICU clinical policy and the Resuscitation Council UK Guidelines.

After SSEP recording

After the SSEP recording the result of the N20 potential will be disclosed to the ICU clinical team as it happens currently as per the established Derriford ICU care and that will not be part of the study.

In the context of the research study:

For those patients who informed consent is obtained from their next of kins and are enrolled in the study, a copy of each recording will be produced for the study purposes by one member of the study team who is not participating in the interpretation of the recording. This copy will be anonymised by giving a specific number for the study. The date of the recording and the time will be available on the copy. The specific study number of each recording will correspond to the specific patient and will be kept on a list not accessible by the neurophysiology study team members who will perform the interpretation of the recording for the study purposes.

After each copy has been anonymised and added in the study databank, the anonymised copy will become available to the first and to the second interpreter [both members of the study team (neurophysiology)] who will interpret the recordings with regards to the presence and absence of the N20 and P25/30 SSEPs and they will record the results of their interpretation in the results databank. The two interpreters will be blinded for the personal and the clinical details of the patient. Also each one of the interpreters will not be aware about the result of the interpretation of the other. The ICU clinicians will not be aware about the results of the P25/30 interpretation as this will be part of the study and should not be disclosed to them during the conduction of the study. In this way, the P25/30 interpretation results will be impossible to affect the treatment of the patients and / or any of the clinical decisions made about them by the ICU clinicians who will strictly be kept unaware about the results of the P25/30 SSEPs.

In the unlikely event that there was a discrepancy in interpretation of the SSEP recording between the two delegated interpreters, then a third member [not a member of the study team] of the Neurophysiology team would be asked to review the anonymised recording only in order to decide about the result. The data of the patients as well as the date of recording and the results of the interpretation of the two study team interpreters would not be disclosed to the third independent interpreter.

Interpretation of the SSEP recording for study purposes in details

Cortical N20 response is to be described as bilaterally absent (which is a good predictor of poor neurological outcome), or in other cases it may be present on one or both sides.

If the cortical N20 response is absent, the presence of the peripheral N9 and N13 response must be present to ensure that the response has arrived at the cortex. Cervical lesions need to be excluded if Cortical N20 response is absent.

The results of the SSEP from the patients enrolled to the study will be additionally interpreted for the presence or absence of the P25/30 waveforms. The additional interpretation for the study purposes will be as follows:

1. Check that baseline is clear and stable.
2. Check that all measured components are reproducible (should be possible to superimpose waves)
3. Check that peripheral nerve (N9) potential is present
4. Check that cervical spinal (N13) potential is present
5. Check that scalp (N20) potential is present and higher than 0.5 microvolts.
6. Check that scalp (P25/30) potential is present and higher than 0.5 microvolts..
7. As the P25/30 potential could be generated in the absence of N20 as they come from two distinct areas of the brain cortex, the presence of either the P25/30 or the N20 would be confirmed when the amplitude of each one is equal or higher than the amplitude threshold [0.5 microvolts] used for the analysis of the SSEPs. The presence and the amplitude of P25/30 will not be dependent on the presence of N20 in the same recording as each one of them can exist in the absence of the other
8. Measurement of the amplitude of recorded P25/30 and N20 and their combinations. Test if there is a correlation of the recorded amplitudes and their ratio [P25/30 to N20] with the positive predictive value of N20 for the favourable neurological outcome.

Explanation clarification between the usual Derriford ICU post cardiac arrest care and what additionally will be done for the research study purposes

[figure not shown]

Figure 3. Explanation-clarification of the usual Derriford ICU post cardiac arrest care and what additionally will be done for the research study purposes

During the conduction of the study the patient's confidentiality and the unbiased analysis / interpretation of the SSEP recordings of the patients will be continuously ensured by the fact that once enrolled in the study their personal data will be replaced by a study number that will be representative of them. Only the members of the team that collect the data and do not take part in any interpretation of the results of the SSEPs and are not involved as clinicians in the clinical care of the patient will be aware about the correspondence between the study number and the personal and clinical details of each patient. The members of the study team that will be SSEP interpreters will be blinded for any clinical and personal data of the patients and the clinical ICU team will be not aware about the result of the P25/30 study interpretation.

After the SSEP recording has been conducted, between 24 and 36 hours post ROSC, the patients will be followed up by members of the study team. Those members of the team will assess the patients, by CPC and by performing full neurologic clinical examination, on the day of ICU discharge and on the

day of their discharge from Derriford Hospital. The online system SALUS of Derriford hospital will be used to follow up the patients after their discharge from ICU and before their discharge from the hospital.

The study team has already worked collaboratively with the IT and SALUS teams members and they have developed an effective way of patients follow up for the study purposes.

Through SALUS system, the members of the study team responsible for the patients follow up will be notified for the planned patients' discharge date in order the patients to be assessed by a study team member before they leave the hospital. The neurologic outcome, assessed with the Cerebral Performance Category [see figure 1 on the Appendix], will be recorded on the day of Hospital discharge [within the last 24 hours before discharge].

If a study participant died on ICU as a result of severe brain dysfunction or after the decision of ICU Consultant to be withdrawn from invasive organ support due to extremely poor prognosis and futility of further continuation of treatment, then, the discharge CPC would be the most recently recorded, after the patient have remained consistently off sedation [for a period of time varied for different sedatives or combination of sedatives].

Specifically, in a case that the ICU Consultant in charge considered withdrawing the invasive organ support in one of the study participants due to extremely poor prognosis, then the ICU consultant should notify the ICU research nurse in order one member of the team to perform the CPC score recording. The assessment by CPC must always take place before the decision for withdrawal of treatment is implemented and strictly before the palliative pathway is initiated. If the study team members failed to be notified by the ICU consultant about the withdrawal of treatment and the Palliative pathway is initiated before patient's CPC and neurologic examination recorded then the patient will be excluded from the study.

If a participant died unexpectedly from another cause rather than severe brain dysfunction and / or withdrawal of invasive organ support, then the most recent CPC before death [if possible to be recorded] will be based on the last available clinical assessment off sedation and will be considered as indicative of neurologic outcome for the patients. In case the CPC could not be assessed, the patient would be excluded from the study analysis.

If patients die on ICU while still on sedation and before being possible to assess their CPC then they will be excluded from the study analysis as the assessment of their outcome based on CPC will not be possible.

The Results of the CPC assessment and the outcome of the patients will be stored in the general study databank for further analysis.

The members of the study team with the help of the Derriford Hospital IT team have already created a study team folder on the hospital computer system. Rights to access the study folder have been

provided by Derriford hospital IT only and strictly to the study team members. The access to the folder is password protected. Each member of the study team must protect the patients' confidentiality and treat the data safely as per Good Clinical Practice and Research Governance Principles.

The study folder will contain four separate databanks: The first databank will contain the personal data of the patients [Name, Age, Hospital number, next of kin, and contact details] and their corresponding study numbers by which the patients will be known to all the members of the study team. During the conduction of the study, specific members of the study team will be responsible for the creation and management of this databank and only they will have access to this during the conduction of the study.

The second databank will contain all the clinical data that will be recorded for each patient [represented by a study number on this databank] on the day of ICU admission, the day of ICU discharge and the day of hospital discharge [see below for further information regarding clinical data expected to be collected for each patient].

The third databank will contain the results of the interpretation of the SSEP recordings with regards to P25/30 and N20 SSEPs. This databank will be accessible during the study conduction only by the study team members who will be the interpreters of the SSEP recording.

The fourth databank will contain the results of the neurologic outcome of the patients, in the form of Cerebral Performance Category recorded on ICU discharge day and on hospital discharge day.

At the End of the study, all data will be merged and statistically analysed and from the result of this analysis one or more relevant manuscripts must be submitted to a peer-review journal within the first 4 months after the completion of the study.

For each one of the patients-participants, the following clinical data must be collected prospectively, during the conduction of the study [at different stages i.e. at the time of enrolment and follow up] and must be kept safely in an anonymised form in a suitable database [see above for explanation]. The principles of patients' confidentiality and privacy must be applied at all times.

1. Age
2. Gender
3. Comorbidities [Scored by Charlson Comorbidity Index (see figure 3 on the Appendix)]
4. Pre-admission performance status [Assessed by the ECOG/WHO performance status score (see figure 2 on Appendix)]
5. Cardiac Arrest Rhythm [Rhythm that was initially recorded after cardiac arrest, usually at scene]
6. Bystander – witness of cardiac arrest and Cardiopulmonary resuscitation

7. Anoxic time [total time between cardiac arrest was noted and ROSC]. If multiple episodes of cardiac arrest then the sum of all anoxic times to be considered.
8. GCS before intubation [total or with components if available]
9. Aetiology of cardiac arrest [cardiac or non-cardiac or unknown]
10. CT scan report if performed because it was clinically indicated
11. Cerebral performance category at ICU discharge and Hospital discharge.
12. Date of death, number of days post ROSC that death occurred
13. ICU length of stay, hospital length of stay
14. Time of SSEP performed [hours post ROSC]
15. Time between ROSC and ICU admission,
16. First 24 hours post ROSC: mean SpO₂, mean PaO₂, mean PaCO₂, mean HR, mean BP, mean Glucose levels, mean Lactate levels, mean pH, mean BE, Urea and Creatinine levels, liver function tests: ALT, INR, Bil and ammonia in patients with pre-admission acute or chronic hepatic dysfunction], Plasma Na levels, Temperature, SOFA Score, APACHE II score.

No particulars tests needed for the study purposes. The aforementioned tests are performed and the aforementioned clinical data are recorded for all patients admitted to Derriford ICU after out of hospital cardiac arrest as part of daily clinical practice.

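### The recording date and time stay on the traces read by the two main interpreters, which weakens the blinding promised for the P25/30 reading

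*Combined protocol and SAP*

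**What the plan says.** Under After SSEP recording, section 4.1 has a study team member who does not interpret recordings make an anonymised copy of each one. The copy carries a study number, and "The date of the recording and the time will be available on the copy". It goes to two interpreters, both neurophysiology members of the study team, who each read N20 and P25/30 without knowing the other's result.

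The plan states that "The two interpreters will be blinded for the personal and the clinical details of the patient". The list linking study numbers to patients "will be kept on a list not accessible by the neurophysiology study team members" who do the reading. Later in section 4.1 the promise is repeated: "The members of the study team that will be SSEP interpreters will be blinded for any clinical and personal data of the patients". Section 5 says again that the interpreting scientists will not learn clinical data at any point.

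If the two readings differ, a third neurophysiologist from outside the study team decides. For that reader the plan lists "The data of the patients as well as the date of recording and the results of the interpretation" by the first two readers as items that "would not be disclosed to the third independent interpreter". Only the date is named there; the time of day is not mentioned.

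On routine care, the opening of section 4.1 says that the hospital's neurophysiology team both records and analyses the SSEPs. Of the bedside reading it says: "Immediately after SSEP recording, each recording will be interpreted for N20 and the result will be disclosed to the ICU clinicians".

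**The concern.** P25/30 presence is the index test, and its sensitivity, specificity and predictive values are the second primary objective (section 2). Reading it takes judgement: the interpreter decides whether the baseline is clear, whether the waves reproduce, and whether a peak reaches 0.5 microvolts. Blinded reading is the main protection against a borderline call being swayed by what the reader knows of the patient.

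The plan relies on replacing personal details with a study number. A date and time left on the same sheet offers a way round that. The two readers whose calls normally stand see the stamp, while the reader used only for discrepancies is not given the date. The plan gives no reason for the difference. It does not bar a study interpreter from having made or clinically read the same recording, and it does not fix when the study reading takes place relative to the CPC assessment. A reader who could place the trace might therefore know something of the clinical course.

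**Working it through.** The plan states no figure on this point, so there is none to reproduce. The check has two parts.

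**1. The passages side by side (section 4.1 unless noted)**

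- First and second interpreters: blinded to personal and clinical details; link list closed to them; date and time visible.
- Third reader: patient data, recording date and the first two readings withheld.
- Routine recordings: made and analysed by the same hospital's neurophysiology team.
- Separation of bedside and study roles for an individual recording: not stated.
- Timing of the study reading relative to CPC: not stated.

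The closed list blocks the route from study number to patient. It does not block the route from date and time to patient.

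**2. How distinctive a date is**

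Inputs: minimum sample size 115 (section 7.1 a); planned number 120 and duration 24 to 36 months (section 3); 200 OHCA admissions to the unit in 3 years (section 1.1). I take 36 months as 1,095.75 days and 24 months as 730.5 days.

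Assume Poisson arrivals and one recording per patient. With daily rate r = n / days, the probability that no other case shares a given recording's date is exp(−r), and that none falls within the same hour is exp(−r/24).

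| Basis | Per month | r per day | exp(−r) | exp(−r/24) |
|---|---|---|---|---|
| 115 in 36 months | 115/36 = 3.2 | 115/1,095.75 = 0.105 | 0.900 | 0.9956 |
| 120 in 36 months | 120/36 = 3.3 | 120/1,095.75 = 0.110 | 0.896 | 0.9954 |
| 120 in 24 months | 120/24 = 5.0 | 120/730.5 = 0.164 | 0.849 | 0.9932 |
| 200 in 36 months | 200/36 = 5.6 | 200/1,095.75 = 0.183 | 0.833 | 0.9924 |

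A date alone would be unique among these cases about 83% to 90% of the time, and date with hour more than 99% of the time. The last row counts all OHCA admissions, not only those alive, eligible and recorded at 24 to 36 hours, so it is an upper figure for the rate. SSEP sessions for other patients are not counted, because the documents give no number for them.

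**The case against.** The strongest reply is that the plan already has several layers of protection. A non-interpreter makes the copies, the link list is closed to the readers, those who hold the link take no part in interpretation, outcomes sit in a different databank from the readings, and two mutually blinded readings are made. A date identifies nobody without a key from date to patient, and no passage says that the two interpreters have one. Copies become available once anonymised and filed, which is compatible with reading before the discharge CPC exists.

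Much of this stands, and it rules out several stronger readings.

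- A reader might infer that the interpreters will identify patients. The documents do not say that they made or clinically read these recordings. They only fail to exclude it.
- A reader might infer that 83% to 90% is the chance of identifying a patient. It is the chance that a date is unique among cases. Identification also needs session memory or access to a log.
- A reader might infer that the stamp does harm by revealing the disclosed N20 result. Both interpreters must read N20 from the same trace as P25/30, so they see it whatever the stamp shows.
- A reader might infer that hiding the date from the third reader shows that the plan regards it as a blinding risk. No motive is given. That reader is outside the study team, so confidentiality would explain the difference equally well.

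What remains is that leaving the stamp on is a stated rule, and none of the listed safeguards closes the route from stamp to patient for someone with memory of the session or access to a log.

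**Conclusion.** The point holds as a weakness in the blinding, not as a demonstrated breach. At about 3 to 6 cases a month in one hospital, the date and time are distinctive enough that a reader with session memory or log access could link a trace to a patient and that patient's clinical course. The two readers exposed to this are the ones whose calls normally determine the index test.

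The uniqueness figures rest on Poisson arrivals, one recording per patient and the protocol's own rates. The step from a unique date to a known patient rests on access or memory that the documents neither state nor exclude. The direction and size of any effect on sensitivity or specificity cannot be derived. The change is still worth making, because it protects a blinding that the plan itself promises and costs very little.

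**What to change.** Replace the sentence in section 4.1 (After SSEP recording) that leaves date and time on the copy with one saying that both are masked on the copies for all three readers and that only the study number is shown. Extend the third-reader sentence to name the time as well as the date. The waveform checks listed for the study reading do not use either. Hours from ROSC to SSEP are item 14 of the clinical data list in section 4.1 and can be merged by study number at analysis.

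The cost is one field to mask when the non-interpreting team member makes each copy. Traceability is kept through the study-number list. Release of copies in random order should not be required: it would mean holding copies back and could push readings past the point at which outcomes are known.

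Masking narrows the route but does not close it. A reader may still recognise a trace that he or she recorded, or know roughly when a newly arrived copy was made.
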